6.5.2. Weekly Visits through Radiation Therapy

During regular visits with medical staff, study subjects will also meet with study staff. Study staff will obtain photographs of the area of irradiation and collect the daily dairy forms. Study personnel will collect vital signs and the physician's assessment of the presence and quality of radiation dermatitis using the RTOG scale as well as the physician's assessment of skin dryness, appearance of inflammation, and the skin's natural barrier. Any adverse events will be noted and addressed. Subjects will complete the Dermatology Life Quality Index. Study personnel will provide KeraStat Cream, as needed, to subjects randomized to receive KeraStat Cream. Subjects randomized to standard of care will follow the instructions of their radiation oncologist. Study personnel will provide subjects with a daily diary form where subjects will note symptoms or treatment details of concern.

6.5.3. Post-Radiation Therapy/Close-Out Visit

During a final follow up visit with medical staff (estimated at 4 to 6 weeks post radiation therapy termination), or if the subject terminates the study, the study subject will meet with study staff. Study staff will obtain photographs of the area of irradiation and collect the daily dairy forms. Study personnel will collect vital signs and the physician's assessment of the presence and quality of radiation dermatitis using the RTOG scale as well as the physician's assessment of skin dryness, appearance of inflammation, and the skin's natural barrier. Any adverse events will be noted and addressed. Subjects will complete the Dermatology Life Quality Index.

6.6. Criteria for Study Termination

The Sponsor reserves the right to temporarily suspend or prematurely discontinue this study at any time for reasons including, but not limited to, safety or ethical issues or severe non-compliance. If the Sponsor determines such action is needed, Sponsor will discuss this with the Investigator (including the reasons for taking such action) at that time. When feasible, Sponsor will provide advance notification to the Investigator of the impending action prior to it taking effect.

Version: 00

Effective Date:

03-01-2018

The Sponsor will promptly inform the Investigator and/or institution conducting the study if the study is suspended or terminated for safety reasons and will also inform the regulatory authorities of the suspension or termination of the study and the reason(s) for the action. If required by applicable regulations, the Investigator or KeraNetics/KeraNetics designee, depending on whether the Institutional Review Board (IRB) is a central or local IRB, must inform the IRB promptly and provide the reason for the suspension or termination.

If the study is prematurely discontinued, all study data must be returned to Sponsor. In addition, arrangements will be made for all unused study device(s) to be destroyed or returned in accordance with the applicable procedures for the study.

7. SELECTION AND WITHDRAWAL OF SUBJECTS

7.1. Subject Inclusion Criteria

At the Screening Visit (Visit 1), subjects must meet all of the following criteria:

- 1. Age ≥ 18
- 2. Female
- 3. Diagnosis of breast cancer and scheduled to receive 4 to 6 weeks of radiation therapy (radiation dose of 42 Gy or more)
- 4. Able and willing to sign protocol consent form
- 5. Able and willing to document symptoms and treatment details as often as needed, not to exceed daily notes
- 6. Able and willing to have photographs of the affected area taken regularly

7.2. Subject Exclusion Criteria

To participate in the study, subjects must not meet any of the following criteria:

- 1. Women who are pregnant, lactating/nursing or plan to become pregnant
- 2. Previous radiation therapy to the area to be treated with radiation therapy
- 3. Receiving palliative radiation therapy
- 4. Unhealed or infected surgical sites in the irradiation area
- 5. Patients undergoing cytotoxic chemotherapy or concurrent Herceptin as part of overall treatment plan (tamoxifen/aromatase inhibitor allowed)
- 6. Use of oral corticosteroids or topical corticosteroids in the irradiation area
- 7. Subjects with an autoimmune disease affecting the skin (e.g., scleroderma, systemic lupus erythematosus, psoriasis) are excluded. A history of other autoimmune disease that does not have direct skin involvement (e.g. rheumatoid arthritis, inflammatory bowel disease, multiple sclerosis) does not exclude participation on the study unless the subject

Version: 00

Effective Date:

03-01-2018

requires active treatment with systemic steroids, immune suppression or biologic agents, or systemic chemotherapeutic agents (methotrexate or cyclophosphamide).

- 8. Skin disease in target irradiation area
- 9. Known allergy to the standard of care or ingredients in KeraStat Cream

7.3. Subject Completion and Withdrawal

7.3.1. Subject Completion

A subject will be considered to have completed the study if they complete the entire study through the final evaluation (Visit 5 or 6).

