1. SYNOPSIS

Name of Company:Name of Product:Type of Study:KeraNetics, LLCKeraStat® CreamClinical Proof of Concept

Title of Study: Pilot Study: KeraStat® Cream for Radiation Dermatitis

Investigator(s): [name], PhD; [name], PhD

Study Period: Estimated screening expected to start March 2018; Expected completion September 2018

Phase of Development: Design & Development (Phase 3 of Design Control)

Objective(s):

Primary:

- To assess feasibility (compliance of use)
- Collect data for designing a larger future trial evaluating KeraStat Cream

Secondary:

- To assess the safety and tolerability of KeraStat Cream in subjects at risk of radiation dermatitis
- To assess the effectiveness of KeraStat Cream compared to standard of care to manage the symptoms of radiation dermatitis in subjects being treated with radiation therapy
- To estimate amount of KeraStat Cream used per patient and coverage on skin

Methodology: This is a randomized, open label study.

Number of Subjects:

Sufficient subjects will be screened and enrolled such that 24 total subjects, 12 subjects per treatment group, will complete the study through the Follow-Up Visit. With 12 participants in each treatment group, we will be able to calculate a 95% confidence interval around the compliance rate in each group with a maximum margin of error of 0.283. Comparisons between groups for effectiveness will have 80 percent power to detect a difference of 1.2 standard deviations. Results of the current study are intended to provide descriptive endpoint data to inform the design of a future clinical evaluation of product effectiveness.

Study Overview:

Study Periods:

The length of study participation for a subject is about 8-12 weeks, depending on the length of radiation treatment. The study will extend 4-6 weeks beyond the end of radiation therapy. The study will begin with a Screening Visit during treatment planning followed by weekly assessments during radiation therapy, and a follow up visit 4-6 weeks after completion of therapy. There is a total of 5-7 visits.

Study Assessments:

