At the Screening/Baseline Visit (Visit 1, Week 0), following informed consent, initial eligibility will be verified per the inclusion/exclusion criteria and demographics and brief medical history will be collected. Subjects will be randomized to receive standard of care or KeraStat Cream. A physical exam and photograph of the area to be irradiated will be obtained, and subjects will complete the Dermatology Life Quality Index.

During the course of radiation therapy (4-6 weeks) and for the duration of the post RT treatment period (4-week follow up), subjects will complete a daily diary detailing symptoms and treatment details. Weekly from week 2 of RT until the end of treatment, study staff will assess the subject for radiation dermatitis by recording the RTOG for Radiation-Induced Acute Skin Toxicity scores and taking photographs. The same evaluation will be performed at the follow up visit after treatment. Subjects will complete the Dermatology Life Quality Index at each visit.

Inclusion Criteria:

Subjects must meet all of the following criteria:

- 1. Age ≥ 18
- 2. Female
- 3. Diagnosis of early stage (stage 0-2) breast cancer and scheduled to receive 4-6 weeks of fractionated radiation therapy as part of breast conserving therapy following lumpectomy

Exclusion Criteria:

Version: 00 03-01-2018

Effective Date:

Name of Company:Name of Product:Type of Study:KeraNetics, LLCKeraStat® CreamClinical Proof of Concept

To participate in the study, subjects must not meet any of the following criteria:

- 1. Previous radiation therapy to the area to be treated with radiation therapy
- 2. Receiving palliative radiation therapy
- 3. Low dose radiation protocol
- 4. Unhealed or infected surgical sites in the irradiation area
- 5. Patients undergoing cytotoxic chemotherapy or concurrent Herceptin as part of overall treatment plan (tamoxifen/aromatase inhibitor allowed)
- 6. Use of oral corticosteroids or topical corticosteroids in the irradiation area
- 7. Subjects with an autoimmune disease affecting the skin (e.g., scleroderma, systemic lupus erythematosus, psoriasis) are excluded. A history of other autoimmune disease that does not have direct skin involvement (e.g. rheumatoid arthritis, inflammatory bowel disease, multiple sclerosis) does not exclude participation on the study unless the subject requires active treatment with systemic steroids, immune suppression or biologic agents, or systemic chemotherapeutic agents (methotrexate or cyclophosphamide).

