6. INVESTIGATIONAL PLAN

6.1. Overall Study Design

This is a single site, between subject, open-label comparison pilot study to assess the feasibility and effectiveness of KeraStat Cream in managing RT skin toxicity. The length of study participation for a subject is 8-12 weeks depending on when a subject returns for her final follow-up evaluation. The Study Design Schematic is shown below in Figure 1 with the Acceptable Study Windows in Table 2.

Sufficient subjects will be screened such that 24 total subjects will complete the study. Patient compliance is expected to be good, so a target recruitment of 26 subjects is desired.

Once a RT patient is determined to be a candidate for inclusion in this study, they may be approached for consent to participate. A total of 26 breast cancer patients scheduled to receive RT will be recruited and consented.

RT will begin 4 to 10 weeks after surgery; the targeted volume will be the ipsilateral breast with or without regional lymph nodes. Once the patient has consented to participate in the study, their baseline pre-RT assessments can be completed during the radiation treatment-planning process.

Patients are generally treated with RT Monday through Friday, with weekends and holidays off, for approximately 4 to 6 weeks. Patients will be provided with KeraStat Skin Cream for application as often as needed but at least twice daily, morning and evening.

During the course of treatment, the patient sees the radiation oncologist weekly in clinic to review the patient's treatment course, monitor the skin's appearance after application of KeraStat Skin Cream or standard of care, and answer questions. Breaks in the treatment schedule should be avoided whenever possible, but breaks necessitated by RT skin toxicity or for other reasons will be recorded. The radiation oncologist will see each patient in follow-up 4-8 weeks after completing RT to assess the patient for RT-induced skin and other toxicities that may have occurred.

Version: 00

Effective Date: 03-01-2018

Figure 1: Study Design Schematic

Table 2: Acceptable Study Windows

Visit	Day Visit	Acceptable Visit Window
Screening (Visit 1)	Day 1	None
Baseline (Visit 1)	Day 1	None
First evaluation (Visit 2)	RT Day 8	±2 days
Second evaluation (Visit 3)	RT Day 15	±2 days
Third evaluation (Visit 4)	RT Day 22	±2 days
Fourth evaluation (Visit 5)	RT Day 29	±2 days
Fifth evaluation (Visit 6)	RT Day 36	±2 days
Final evaluation (Visit 7)	Post RT Day 30	±14 days

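### Do the wrong visit number in 7.3.1, the differing follow-up ranges and the unnamed DLQI visit leave completion or the analysis undefined?

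*Combined protocol and SAP*

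**What the plan says.** Completion is defined in section 7.3.1: "A subject will be considered to have completed the study if they complete the entire study through the final evaluation (Visit 5 or 6". In section 6.1, "Table 2: Acceptable Study Windows" has a row labelled "Final evaluation (Visit 7", placed at day 30 after radiotherapy (RT) with 14 days allowed either side. In the same table "Fifth evaluation (Visit 6" is an on-treatment evaluation at RT Day 36, and Visit 5 is one at RT Day 29. The synopsis fixes no number for the last visit; it says "There is a total of 5-7 visits".

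On timing, the synopsis plans "a follow up visit 4-6 weeks after completion of therapy", and section 6.5.3 gives the same range as an estimate. The text of 6.1 says "The radiation oncologist will see each patient in follow-up 4-8 weeks after completing RT". The Study Assessments part of the synopsis and section 11.5 both speak of four weeks of follow-up.

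On outcomes, the synopsis schedules RTOG scoring "Weekly from week 2 of RT until the end of treatment" and again at follow-up. DLQI is completed at every visit (11.3). Section 12.1 plans t-tests on both scores without naming a visit. The synopsis criteria list maximum severity for RTOG and change from baseline for DLQI, with no visit for the DLQI change.

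**The concern.** Read literally against Table 2, the number in 7.3.1 would let a patient count as a completer at an on-treatment visit, with no post-RT assessment. The study aims for 24 completers, and 12.1 uses the term completion rate when it describes feasibility, so a wrong label might seem to reach the primary objective.

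The follow-up ranges raise a second worry. A site that followed the text of 6.1 could see a patient on a day Table 2 does not accept. Follow-up skin reaction, DLQI and skin appearance would then be averaged over different stages of recovery, in a study meant to inform a larger trial.

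Third, a DLQI test with several possible visits leaves room to choose the visit after the data are seen.

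**Working it through.** **1. The plan's own figures.** Section 12.2 gives 12 per group, a maximum margin of 0.283, and 80 percent power for 1.2 SD.

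- Margin: 1.96 × √(0.25/12) = 0.2829, which agrees.
- Power: two-sample t-test, 12 per group, 1.2 SD, two-sided 0.05 (an assumption; the plan states neither level nor sidedness) = 0.802, which agrees.

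Neither formula contains a visit number or a window.

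**2. The visit number.** Take a Monday-to-Friday course of w weeks that starts on a Monday and has no breaks. The last RT day is 7(w − 1) + 5. Count the Table 2 evaluations up to that day, then add the baseline and final visits.

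| Course | Last RT day | On-RT evaluations | Total visits | Post-baseline DLQI scores |
|---|---|---|---|---|
| 4 weeks | 26 | Days 8, 15, 22 | 1 + 3 + 1 = 5 | 4 |
| 5 weeks | 33 | adds Day 29 | 1 + 4 + 1 = 6 | 5 |
| 6 weeks | 40 | adds Day 36 | 1 + 5 + 1 = 7 | 6 |

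The totals match the synopsis's count of 5 to 7. The number in 7.3.1 is therefore a running count that fits 4- and 5-week courses and omits the 6-week case. It never matches Table 2's fixed label. The counts shift with the starting weekday: 20 fractions begun on a Wednesday end on RT Day 28, and Table 2 allows its Day 29 visit from Day 27.

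**3. What completion feeds.** The sentence in 12.1 that mentions a completion rate goes on to define the measure as averaging 10 or more applications per week, and 11.1 calls it the compliance rate. Section 12.3 keeps the data of patients who withdraw. Enrolment is capped at 26 (12.2) and patients are not replaced (7.3.3). No planned estimate uses the visit number.

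**4. The follow-up windows, in days after RT.**

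- Table 2: 30 ± 14 = days 16-44, which is 29 days.
- Synopsis and 6.5.3: 4-6 weeks = days 28-42, which is 15 days, all inside Table 2.
- Text of 6.1: 4-8 weeks = days 28-56, which is 29 days; 56 − 44 = 12 of them fall after Table 2 closes.
- Common to all four places: days 28-42.
- Table 2 opens 28 − 16 = 12 days before week 4.
- Union of all ranges: days 16-56, which is 41 days, against 29 under Table 2 alone.

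Section 6.1 also gives total participation of 8-12 weeks. With 4-6 weeks of RT, 4 + 4 = 8 and 6 + 6 = 12, whereas 6 + 8 = 14 overshoots. The 4-8 week sentence is thus out of line with its own section as well as with Table 2.

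**5. The t-tests.** Maximum RTOG severity needs no single visit, so the synopsis settles that measure. For DLQI the measure is settled and the visit is not, with 4 to 6 candidates. If six visits were each tested at 0.05 and the tests were independent, the chance of at least one false positive would be 1 − 0.95⁶ = 0.26. Scores from the same patient at successive visits are likely to be positively correlated, so this illustration probably overstates it.

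**The case for a change.** The best case for amending is that every discrepancy is real and the repair is wording only. A 6-week course is eligible, so the number in 7.3.1 is wrong or incomplete under any numbering. A site can obey the text of 6.1 and still fall outside the accepted window. The statements of four weeks of follow-up overlap days 28-42 only at day 28. Section 11.5 plans a proportion with a confidence interval at each of four time points without listing them, while the weekly schedule gives 4, 5 or 6 assessments. The DLQI visit could be picked after the results are known.

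The clerical points stand: the label is wrong, and 6.1's range is out of line with the other statements. So does the absence of a named DLQI visit. The consequences do not follow:

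- The label cannot override the words around it, or the synopsis's requirement that completers reach the follow-up visit.
- Mixing recovery times comes mainly from Table 2's deliberate 14 days either side, a fair allowance for a single-site pilot tied to routine clinic visits. No section links visit timing to arm, and none removes an out-of-window assessment from the analysis.
- The four time points equal the count for a 4-week course and may be a subset for longer ones. The study schematic (Figure 1) is not visible in the text available here, so an omission cannot be shown.
- The 10 weeks in 11.2 (day 70) is an upper limit, and it contradicts nothing by lying beyond the last visit.
- The multiplicity illustration would matter for a confirmatory claim. The synopsis presents the results as descriptive input to a later trial.

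**Conclusion.** The discrepancies are confirmed, but no change to the plan follows. The number in 7.3.1 is a clerical slip with no effect on who has completed. The follow-up statements differ by up to 12 calendar days at the late end, yet days 28-42 satisfy the synopsis, Table 2, 6.5.3 and the text of 6.1; which range the sponsor intends is not for this review to choose. The unnamed DLQI visit is a gap that analysts can fill sensibly by tabulating change from baseline at each visit by group.

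Compliance, the 0.283 margin, the 80 percent power and the handling of withdrawals are untouched. The effect of timing on the follow-up skin and DLQI estimates cannot be sized, because the documents give no recovery data; 12 days is a count of calendar days, not of expected visits. The conclusion assumes that the study is reported as the descriptive pilot it says it is. The visit counts assume a Monday start without breaks. The power check assumes a two-sided 0.05 test.

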7.3.2. Patient Withdrawal (Premature Discontinuation from the Study)

A documented effort must be made to determine why a subject fails to return for the necessary visit or is dropped from the study, and the reason for withdrawal must be recorded in the source documents and case report form (CRF). A subject may withdraw or be removed from the study for any of the following reasons and will be treated as considered appropriate by the Investigator:

- Subject request (for any reason)
- In the opinion of the Investigator, continuation is not in the best interest of the subject
- A serious or unexpected AE occurs such that continuation in the study is inappropriate
- Pregnancy
- RT is stopped
- In the opinion of the Sponsor, continuation is not in the best interest of the subject

If a subject is prematurely discontinued from participation in the study for any reason, the Investigator must follow up on all ongoing adverse events (if any).

In the event a subject is prematurely discontinued from the study due to an AE, or unexpected AE or serious adverse event (SAE) (as defined in Section 11.5.1), the procedures stated in Sections 11.3-11.9 must be followed.

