11.8.3. Protocol Deviations Due to an Emergency or Adverse Event

Any subject experiencing an emergency or adverse event requiring immediate medical attention will receive appropriate medical management by medical staff at the site and at other clinical sites as indicated. These events will be reported to Sponsor as soon as possible. If the medical management results in departure from the study protocol, the Sponsor will be responsible for granting permission for the subject to continue in the trial if the subject is able to return to study protocol adherence in a timely fashion. If the subject cannot return to the study protocol in a timely fashion, then the subject will be discontinued from the study.

KeraNetics, LLC. CONFIDENTIAL Page 23

Version: 00

Effective Date:

03-01-2018

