14.2. Protocol Modifications

The initial protocol as well as all protocol amendments must be signed and dated by the Investigator and approved by the IRB prior to implementation of the original protocol and any amendment. The Principal Investigator must submit all protocol modifications to the IRB, as applicable for specific Investigators, or applicable local regulatory authority.

Departures from the protocol will be determined as allowable on a case-by-case basis or in event of an emergency involving subject safety. The Investigator or other physician in attendance must contact Sponsor as soon as possible to discuss the circumstances of the emergency. Sponsor, in concurrence with the Investigator, will decide whether the subject should continue to participate in the study. All protocol deviations and the reason for such deviations must be noted on the source document and in the CRF and reported to the IRB as appropriate.

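### Sections 7.3.2 and 11.8.3 offer only removal from the study and do not keep later outcome assessments, so what is lost can depend on toxicity

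*Combined protocol and SAP*

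**What the plan says.** Section 7.3.2 gives a single form of exit: "A subject may withdraw or be removed from the study for any of the following reasons". Besides the subject's own request, the investigator's opinion and pregnancy, the reasons include the stopping of RT and these two:

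- "A serious or unexpected AE occurs such that continuation in the study is inappropriate"
- "In the opinion of the Sponsor, continuation is not in the best interest of the subject"

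Section 11.8.3 adds a route for an emergency or AE that needs immediate medical attention and whose management departs from the protocol: "If the subject cannot return to the study protocol in a timely fashion, then the subject will be discontinued from the study". Section 14.2 covers departures in an emergency: "Sponsor, in concurrence with the Investigator, will decide whether the subject should continue to participate in the study".

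After exit, section 6.5.3 provides a close-out meeting at the final follow-up, "or if the subject terminates the study, the study subject will meet with study staff". It includes photographs, RTOG grade, AEs and DLQI. Section 7.3.2 requires follow-up of ongoing AEs and, for AE exits, points to Sections 11.3-11.9. Section 11.9 requires AEs to be followed to resolution or stabilization. Section 12.3 keeps whatever assessments a withdrawn subject completed, and section 7.3.3 rules out replacement.

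**The concern.** Two decisions are joined that could be kept apart: whether a woman goes on using the study product, and whether the study goes on observing her. When an event related to toxicity ends both, the reason that later data are missing is tied to the outcome under study. RTOG severity, DLQI and the EASR proportion at each time point (section 11.5) are all study outcomes, and the stated purpose is to supply figures for designing a larger trial.

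The loss may also differ by arm. The study is open label, so whoever judges whether a woman continues can know her treatment. Under sections 6.4 and 6.5.1 the control is care as the physician directs. A change of skin product there may therefore stay within protocol, while taking a woman off KeraStat Cream would be a departure. That last step is my inference; the documents do not say it.

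**Working it through.** **The plan's own figures.** Section 12.2 states 12 per group and 80% power for a difference of 1.2 SD. It gives no alpha or sidedness, so I assume two-sided 0.05. The noncentrality is 1.2 / sqrt(1/12 + 1/12) = 2.94 on 22 degrees of freedom, and power is 80.2%, so the stated figure reproduces. The allowance for loss is 26 - 24 = 2 women, or 2/26 = 7.7%.

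**What each route leaves in place.**

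1. *RT stopped (7.3.2, permissive).* Weekly visits run only while RT runs (Synopsis, Study Assessments; 6.5.2), so none remain to be lost. The post-RT evaluation in Table 2 is at stake, partly offset by the termination visit.
2. *Serious or unexpected AE making continuation inappropriate (7.3.2, permissive).* The reference to Sections 11.3-11.9, read literally, takes in DLQI (11.3) and EASR (11.5). It sets no schedule of assessments after exit.
3. *Investigator's or sponsor's opinion (7.3.2, permissive).* The termination visit and follow-up of ongoing AEs apply. Nothing is said on later RTOG or DLQI.
4. *AE needing immediate attention, with no timely return to protocol (11.8.3, mandatory).* RT may be continuing, so weekly visits can be lost too. Example: on a 6-week course Table 2 has six post-baseline evaluations (RT Days 8, 15, 22, 29 and 36, and the post-RT evaluation). If she leaves at Day 22, three remain: Day 29, Day 36 and post-RT.

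**What is kept.** RTOG is recorded weekly (6.5.2) and at termination (6.5.3), and completed assessments stay in the summary (12.3). A grade reached and recorded up to exit therefore counts toward maximum severity.

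**Scale.** One woman is 1/12 = 8.3 points of her arm at a time point. At the background rate of about 30% Grade 2 or worse (section 4.2), 0.30 × 12 = 3.6 such women are expected per arm. The documents give no removal rate, so the following is illustration only. Suppose 4 of 12 women (33.3%) truly have EASR at a late time point:

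- one of the four is absent: 3/11 = 27.3%
- two of the four are absent: 2/10 = 20.0%
- two women are absent whose skin has recovered: 4/10 = 40.0%

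The direction of the error thus depends on the state of the absent women at that time point, which the plan would not observe.

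**Effect on power.** If two women in one arm lack the compared outcome, the noncentrality is 1.2 / sqrt(1/12 + 1/10) = 2.80 on 20 degrees of freedom. Power at 1.2 SD is then 76.0%. This is minor beside the possible bias.

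**The case against.** The strongest reply is that a woman who leaves because of a severe reaction has already had it. This stands. A reader might infer that one or two toxicity exits understate an arm's Grade 2+ incidence by 8.3 to 16.7 points (1/12 to 2/12). The documents do not support that, because the grade is recorded weekly and at termination and is retained. Only worsening after exit escapes the maximum.

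Four other tempting readings also go too far:

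- *RT breaks lead to removal.* Sections 4.1 and 4.2 link severe reactions to treatment breaks, but section 6.1 says only that "breaks necessitated by RT skin toxicity or for other reasons will be recorded". A break is not a removal ground, and no section says that skin toxicity leads to RT being stopped.
- *Any AE leads to removal.* Section 7.3.2 requires a serious or unexpected AE that makes continuation inappropriate, and its wording is permissive. An anticipated skin reaction need be neither serious nor unexpected.
- *Stopping RT forfeits half the assessments.* Weekly visits end with RT, so the count of three of six applies only to the 11.8.3 route.
- *Sections 11.8.3 and 14.2 contradict each other on who decides.* Sponsor permission given with the investigator's concurrence satisfies both.

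It is also fair to say that this is a pilot with feasibility as a primary objective, and that enrolling 26 allows for two losses. The allowance protects the number of completers. It does not supply the later outcomes of the women who left. None of these replies points to a passage that continues scheduled RTOG and DLQI assessment after removal.

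**Conclusion.** The point holds in a limited form. The plan provides removal from the study and does not say that outcome assessment continues beyond a termination visit and AE follow-up. The outcomes exposed are later worsening, later EASR proportions, later DLQI, the post-RT visit and, under 11.8.3, the remaining weekly assessments. Dependence on toxicity follows from the stated grounds. Dependence on arm is possible because the study is open label, but it is not shown. The size is unknown: 8.3 points per woman per time point is a unit of scale, not an estimate of bias, and the direction is not fixed. This is a cheap improvement to the plan, not a defect that undermines the pilot.

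**What to change.** State in 7.3.2 that the listed events do not by themselves end study follow-up. The remaining scheduled RTOG, photograph, DLQI and AE assessments continue through the final post-RT evaluation, unless the subject withdraws consent to follow-up or the investigator judges the assessments themselves not to be in her interest. Align the last sentence of 11.8.3, and 14.2, with this. Name the final evaluation by description, because 7.3.1 calls it Visit 5 or 6 and Table 2 calls it Visit 7. The amendment should say nothing about when the product or RT is stopped or altered.

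The cost is amendment wording in three sections and attendance at visits already scheduled. The downside is that some visits after a woman has stopped the product will be harder to obtain.
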